3. INVESTIGATIONAL PLAN

3.1 Study Design and Duration

This is an open label, multi-site, phase 1/2 study of encorafenib +/- binimatinib + nivolumab + ipilimumab for the treatment of participants with unresectable or metastatic *BRAF*-mutated melanoma in high risk cohorts.

Study participants will consist of metastatic melanoma patients harboring *BRAFV600E/K* mutation without previous frontline therapy or recently started treatment with up to 6 weeks of targeted therapy, or one cycle of immunotherapy (or >6 months from adjuvant therapy). Toxicity from prior treatment must have resolved to ≤ Grade 1 and not included previous Grade 3–4 irAEs that required treatment discontinuous or previous Grade 2 immune-related uveitis or pneumonitis.

Phase I, Cohort 1: Twelve patients will be treated with triple therapy: 300 mg encorafenib and 3mg/kg nivolumab and 1 mg/kg ipilimumab. Dose-limiting toxicity (DLT) for Cohort 1 will be evaluated at week 6.

[figure not shown]
Phase I, Cohort 2: Upfront quadruple therapy (450mg encorafenib, 45mg binimatinib, 3mg/kg nivolumab, and 1mg/kg ipilimumab) will be investigated with twelve patients. DLT for Phase I, Cohort 2 will be evaluated at week 6.

Prior studies with triplet therapies combining anti PD-1/PD-L1, *BRAF*, and MEK inhibition have shown Grade 3–4 AEs occurring from 58%–73%^{5,43,44,68}. These initial cohorts were small and did not use the newer, more potent and specific *BRAF*/MEK inhibitor pair encorafenib/binimatinib. We are allowing an initial DLT rate up to 75% in a continuous Bayesian monitoring protocol (See Statistics Section 8). We anticipate most of the toxicities to be additive and not synergistic and based on earlier recognition and treatment of immunotherapy AEs (see Appendix 6) and very specific AEs from encorafenib and binimatinib (see Appendix 2 and 3), we anticipate being able to create a safe RP2R dosing schedule.

Upon establishment of RP2R schedule, only participants with advanced melanoma who are either treatment naïve in the metastatic setting, have recently started treatment with targeted therapy within the past 6 weeks, or one cycle of immunotherapy, or who have progressed on adjuvant therapy more than 6 months following completion of adjuvant therapy (either *BRAF*-MEK or PD1 Ab) will be eligible for participation in high risk disease cohort expansion (Groups 1 or 2, see Schema below).

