APPENDIX 6 MANAGEMENT ALGORITHMS FOR IMMUNO-ONCOLOGY AGENTS

[figure not shown]
Participants should receive appropriate supportive care measures as deemed necessary by the treating investigator. Where appropriate, these guidelines include the use of oral or intravenous treatment with corticosteroids as well as additional anti-inflammatory agents if symptoms do not improve with administration of corticosteroids. Note that several courses of steroid tapering may be necessary as symptoms may worsen when the steroid dose is decreased. For each disorder, attempts should be made to rule out other causes such as metastatic disease or bacterial or viral infection, which might require additional supportive care. The treatment guidelines are intended to be applied when the investigator determines the events to be related to nivolumab/urelumab or nivolumab/cabirizumab.

It may be necessary to perform conditional procedures such as bronchoscopy, endoscopy, or skin photography as part of evaluation of the event.

- Pneumonitis:

Pulmonary Adverse Event Management Algorithm

Rule out non-inflammatory causes. If non-inflammatory cause, treat accordingly and continue I-O therapy. Evaluate with imaging and pulmonary consultation.

[figure not shown]
Patients on IV steroids may be switched to an equivalent dose of oral corticosteroids (e.g. prednisone) at start of tapering or earlier, once sustained clinical improvement is observed. Lower bioavailability of oral corticosteroids should be taken into account when switching to the equivalent dose of oral corticosteroids

- For **Grade 2 events**, treat with systemic corticosteroids. When symptoms improve to Grade 1 or less, steroid taper should be started and continued over no less than 4 weeks.
- For **Grade 3-4 events**, immediately treat with intravenous steroids. Administer additional anti-inflammatory measures, as needed.

- Add prophylactic antibiotics for opportunistic infections in the case of prolonged steroid administration.
- Diarrhea/Colitis:

GI Adverse Event Management Algorithm

Rule out non-inflammatory causes. If non-inflammatory cause is identified, treat accordingly and continue I-O therapy. Opiates/narcotics may mask symptoms of perforation. Infliximab should not be used in cases of perforation or sepsis.

[figure not shown]

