Patients on IV steroids may be switched to an equivalent dose of oral corticosteroids (e.g. prednisone) at start of tapering or earlier, once sustained clinical improvement is observed. Lower bioavailability of oral corticosteroids should be taken into account when switching to the equivalent dose of oral corticosteroids.

Participants should be carefully monitored for signs and symptoms of enterocolitis (such as diarrhea, abdominal pain, blood or mucus in stool, with or without fever) and of bowel perforation (such as peritoneal signs and ileus).

- All participants who experience diarrhea/colitis should be advised to drink liberal quantities of clear fluids. If sufficient oral fluid intake is not feasible, fluid and electrolytes should be substituted via IV infusion. For Grade 2 or higher diarrhea, consider GI consultation and endoscopy to confirm or rule out colitis.
- For **Grade 2 diarrhea/colitis** that persists greater than 3 days, administer oral corticosteroids.
- For **Grade 3 or 4 diarrhea/colitis** that persists > 1 week, treat with intravenous steroids followed by high dose oral steroids.
- When symptoms improve to Grade 1 or less, steroid taper should be started and continued over no less than 4 weeks.
- Type 1 diabetes mellitus (if new onset, including diabetic ketoacidosis [DKA]) or ≥ Grade 3 Hyperglycemia, if associated with ketosis (ketonuria) or metabolic acidosis (DKA)

Endocrinopathy Adverse Event Management Algorithm

Rule out non-inflammatory causes. If non-inflammatory cause, treat accordingly and continue I-O therapy. Consider visual field testing, endocrinology consultation, and imaging.

Patients on IV steroids may be switched to an equivalent dose of oral corticosteroids (e.g. prednisone) at start of tapering or earlier, once sustained clinical improvement is observed. Lower bioavailability of oral corticosteroids should be taken into account when switching to the equivalent dose of oral corticosteroids.

- For **T1DM** or **Grade 3–4 Hyperglycemia**

Insulin replacement therapy is recommended for Type I diabetes mellitus and for Grade 3-4 hyperglycemia associated with metabolic acidosis or ketonuria.

Evaluate participants with serum glucose and a metabolic panel, urine ketones, glycosylated hemoglobin, and C-peptide.

- Hypophysitis:

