- For **Grade 2** events, treat with corticosteroids. When symptoms improve to Grade 1 or less, steroid taper should be started and continued over no less than 4 weeks. Replacement of appropriate hormones may be required as the steroid dose is tapered.
- For **Grade 3–4** events, treat with an initial dose of IV corticosteroids followed by oral corticosteroids. When symptoms improve to Grade 1 or less, steroid taper should be started and continued over no less than 4 weeks. Replacement of appropriate hormones may be required as the steroid dose is tapered.

- Hyperthyroidism or Hypothyroidism:

Thyroid disorders can occur at any time during treatment. Monitor participants for changes in thyroid function (at the start of treatment, periodically during treatment, and as indicated based on clinical evaluation) and for clinical signs and symptoms of thyroid disorders.

- Grade 2 hyperthyroidism events (and Grade 2-4 hypothyroidism):

[figure not shown]
- In hyperthyroidism, non-selective beta-blockers (e.g. propranolol) are suggested as initial therapy.

Phase I/II study of encorafenib and binimetinib with nivolumab and low dose ipilimumab in metastatic *BRAF* mutant melanoma

- In hypothyroidism, thyroid hormone replacement therapy, with levothyroxine or liothyroinine, is indicated per standard of care.
- **Grade 3-4** hyperthyroidism
 - Treat with an initial dose of IV corticosteroid followed by oral corticosteroids. When symptoms improve to Grade 1 or less, steroid taper should be started and continued over no less than 4 weeks. Replacement of appropriate hormones may be required as the steroid dose is tapered.
- Hepatic:

Hepatic Adverse Event Management Algorithm

Rule out non-inflammatory causes. If non-inflammatory cause, treat accordingly and continue I-O therapy. Consider imaging for obstruction.

Patients on IV steroids may be switched to an equivalent dose of oral corticosteroids (e.g. prednisone) at start of tapering or earlier, once sustained clinical improvement is observed. Lower bioavailability of oral corticosteroids should be taken into account when switching to the equivalent dose of oral corticosteroids.

[figure not shown]
*The recommended starting dose for grade 4 hepatitis is 2 mg/kg/day methylprednisolone IV.

- For **Grade 2** events, monitor liver function tests more frequently until returned to baseline values (consider weekly).
 - Treat with IV or oral corticosteroids

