- For **Grade 3-4** events, treat with intravenous corticosteroids for 24 to 48 hours.
- When symptoms improve to Grade 1 or less, a steroid taper should be started and continued over no less than 4 weeks.

- Renal Failure or Nephritis:

Renal Adverse Event Management Algorithm

Rule out non-inflammatory causes. If non-inflammatory cause, treat accordingly and continue I-O therapy.

[figure not shown]

Patients on IV steroids may be switched to an equivalent dose of oral corticosteroids (e.g. prednisone) at start of tapering or earlier, once sustained clinical improvement is observed. Lower bioavailability of oral corticosteroids should be taken into account when switching to the equivalent dose of oral corticosteroids.

- For **Grade 2** events, treat with corticosteroids.
- For **Grade 3-4** events, treat with systemic corticosteroids.
- When symptoms improve to Grade 1 or less, steroid taper should be started and continued over no less than 4 weeks.

Skin Adverse Event Management Algorithm

Rule out non-inflammatory causes. If non-inflammatory cause, treat accordingly and continue I-O therapy.

[figure not shown]
Patients on IV steroids may be switched to an equivalent dose of oral corticosteroids (e.g. prednisone) at start of tapering or earlier, once sustained clinical improvement is observed. Lower bioavailability of oral corticosteroids should be taken into account when switching to the equivalent dose of oral corticosteroids.

*Refer to NCI CTCAE v4 for term-specific grading criteria.

[^]If SJS/TEN is suspected, withhold I-O therapy and refer patient for specialized care for assessment and treatment. If SJS or TEN is diagnosed, permanently discontinue I-O therapy.

[figure not shown]
Neurological Adverse Event Management Algorithm

Rule out non-inflammatory causes. If non-inflammatory cause, treat accordingly and continue I-O therapy.

Patients on IV steroids may be switched to an equivalent dose of oral corticosteroids (e.g. prednisone) at start of tapering or earlier, once sustained clinical improvement is observed. Lower bioavailability of oral corticosteroids should be taken into account when switching to the equivalent dose of oral corticosteroids.

Myocarditis Adverse Event Management Algorithm

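### Appendix 6 states a longer wait before steroids for Grade 3-4 diarrhea/colitis (more than 1 week) than for Grade 2 (more than 3 days)

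*Combined protocol and SAP*

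**What the plan says.** The diarrhea/colitis part of Appendix 6 has two adjacent bullets on steroids. The Grade 2 bullet applies to an event "that persists greater than 3 days, administer oral corticosteroids". The Grade 3 or 4 bullet applies to an event "that persists > 1 week, treat with intravenous steroids followed by high dose oral steroids". The legible text has no steroid instruction for Grade 3-4 diarrhea/colitis that has lasted a week or less.

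Elsewhere in the same appendix, the Grade 3-4 pneumonitis bullet says "immediately treat with intravenous steroids". The Grade 3-4 bullets for hypophysitis, hyperthyroidism, hepatic and renal events also call for steroids and attach no waiting period.

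The protocol leans on this appendix. Section 3.1 expects to reach a safe regimen partly "based on earlier recognition and treatment of immunotherapy AEs (see Appendix 6"), and section 4.8 says that recognising and managing immune-related events early can lessen severe toxicity.

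**The concern.** One would expect the threshold for starting steroids to fall, or at least not rise, as the event becomes more severe. Here it rises. Between the end of day 3 and the end of day 7, a patient with Grade 2 colitis meets the printed trigger for steroids and a patient with Grade 3 or 4 colitis does not. A site that followed the two bullets as printed would start steroids later in the sicker patient.

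The event is foreseeable in this trial. The protocol's background reports Grade 3 diarrhea in 9% of patients on combined nivolumab and ipilimumab in CheckMate 067, which used the higher ipilimumab dose (sections 1.1.2.1 and 1.4.2). It reports 6.1% Grade 3-4 gastrointestinal events in CheckMate 511 at the 3 mg/kg nivolumab plus 1 mg/kg ipilimumab dose used here (section 1.4.2). Encorafenib with binimetinib adds diarrhea of its own: 36%, all grades (section 1.1.2.2). These figures show that the bullet will matter to some patients. They do not say how many would be treated late.

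**Working it through.** No power, error rate or sample size is involved. The check is a comparison of the stated triggers.

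**Step 1: the two triggers in the diarrhea/colitis text.** Grade 2: more than 3 days. Grade 3-4: more than 1 week, that is, more than 7 days. Difference: 7 − 3 = 4 days, with the longer wait for the more severe event.

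**Step 2: comparison with the rest of Appendix 6.** These are all the conditions with a legible Grade 3-4 steroid bullet.

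| Condition | Grade 2 steroid bullet | Wait, Grade 2 | Grade 3-4 steroid bullet | Wait, Grade 3-4 |
|---|---|---|---|---|
| Pneumonitis | yes | none stated | "immediately treat with intravenous steroids" | none; immediate |
| Diarrhea/colitis | yes | more than 3 days | "that persists > 1 week, treat with intravenous steroids followed by high dose oral steroids" | more than 7 days |
| Hypophysitis | yes | none stated | "events, treat with an initial dose of IV corticosteroids followed by oral corticosteroids" | none stated |
| Hyperthyroidism | no | not applicable | "Treat with an initial dose of IV corticosteroid followed by oral corticosteroids" | none stated |
| Hepatic | yes | none stated | "events, treat with intravenous corticosteroids for 24 to 48 hours" | none stated |
| Renal | yes | none stated | "events, treat with systemic corticosteroids" | none stated |

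Grade 3-4 steroid bullets with a waiting period: 1 of 6. Conditions with a steroid bullet at both levels in which Grade 3-4 waits longer than Grade 2: 1 of 5. Diarrhea/colitis is the exception in both counts.

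The table should not be read as five bullets that all order prompt IV treatment. Only pneumonitis states immediacy. The other four are silent on timing, and the renal bullet asks for systemic rather than specifically IV steroids. The counts cover legible text only. The skin, neurological and myocarditis sections have no legible steroid bullet by grade.

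**Step 3: does another section supply an earlier Grade 3-4 trigger?** Section 4.7 defines a DLT as Grade 3 or worse diarrhea for more than 5 days in spite of optimal treatment, and names steroids as a possible part of that treatment. It thus contemplates earlier steroids but does not instruct a site to give them. Section 4.10 sets when study drug must stop (drug-related, non-skin Grade 3 events lasting more than 7 days, with exceptions that do not name diarrhea; Grade 4 without a duration condition for this event). It does not say when steroids start. Neither section overrides the bullet.

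**The case against.** Four points can be made against this.

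- **The GI algorithm figure is unseen.** It sits directly above these bullets and may give an immediate start for Grade 3-4. This stands as a limit. It does not remove the point: if the figure says to treat at once, figure and bullet conflict; if it repeats the bullet, the inversion is in both. The missing figure is not itself held against the plan.
- **A delay allows infection or targeted-drug diarrhea to be excluded.** Appendix 6 asks for other causes to be ruled out for every disorder, and for Grade 2 it still acts after 3 days. That cannot explain a longer wait for worse disease.
- **Sites may treat earlier.** This is correct. The opening of Appendix 6 leaves supportive care to the treating investigator, the GI text suggests considering GI consultation and endoscopy from Grade 2 upward with no wait, and section 4.7 allows for steroids. A reader might infer that the protocol withholds steroids from severe colitis for a week. The documents do not support that: nothing prohibits an earlier start.
- **The appendix looks carried over.** Its introduction ties the guidance to nivolumab combined with agents not used in this trial. That may explain how the wording arose, but section 3.1 still points to this appendix as part of the safety case.

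A reader might also infer that late steroids would inflate the DLT count, because 7 − 5 = 2 days separate the steroid trigger from the diarrhea DLT line. That holds only if the 5 days in section 4.7 run from onset. The criterion can be read otherwise and allows for earlier steroids, so the documents do not support a claim about the primary endpoint.

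**Conclusion.** The point holds as a defect in one bullet of safety guidance, and it should be fixed. The stated steroid trigger for Grade 3-4 diarrhea/colitis is 4 days longer than for Grade 2, it is the only one of six legible Grade 3-4 steroid bullets with a wait, and no legible text explains or overrides it. Confidence is high for the wording. It is lower for the consequence, which depends on what the figure says and on how literally a site takes the bullet. The number of patients whose steroids would be delayed cannot be worked out from the documents. The ground is patient safety; no endpoint, DLT criterion or sample size is affected.

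**What to change.** Delete the one-week persistence condition from the Grade 3-4 diarrhea/colitis bullet in Appendix 6. IV steroids, followed by high-dose oral steroids, would then start without a waiting period once the event is judged immunotherapy-related and non-inflammatory causes are ruled out. Check the bullet against the GI algorithm figure and make the two agree. Leave sections 4.7 and 4.10 as they are.

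The cost is a one-phrase amendment with IRB/IEC approval under section 9.1.1, the check against the figure, and a notice to sites.
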